7.2 Listing of Figures

Figure Number	Figure Title
14.1.1.1	Mean functional gain and 95% CIs for frequencies 500, 1000, 2000 and 4000 Hz, and PTA4, for the combined group and the CHL/MHL group (ITT Population)
14.1.1.2	Bar chart of the proportion with a difference >0, =0 and <0 of functional gain for frequencies 500, 1000, 2000, 3000 and 4000, and PTA4, for the combined group and the CHL/MHL group (ITT Population)
14.1.1.3	SUBPLOT A: Mean unaided AC threshold and 95% CIs for frequencies 500, 1000, 2000 and Hz, and PTA4 SUBPLOT B: Mean aided sound field threshold and 95% CIs for frequencies 500, 1000, 2000 and 4000, and PTA4 for the combined group and the CHL/MHL group (ITT Population)
14.1.2.1	Bar chart of the mean aided speech recognition (% correct words) and 95% CIs measured in quiet and in noise with the BKB sentence test for the combined group and the CHL/MHL group (ITT Population)
14.1.2.2	Boxplot and mean of the aided speech recognition (% correct words) and 95% CIs measured in quiet and in noise with the BKB sentence test for the combined group and the CHL/MHL group (ITT Population)
14.1.2.3	Bar chart of the mean aided speech recognition (% correct words) and 95% CIs measured in quiet and in noise with the AB[s] short list test for the combined group and the CHL/MHL group (ITT Population)
14.1.2.4	Boxplot and mean of the aided speech recognition (% correct words) measured in quiet and in noise with the AB[s] short list test for the combined group and the CHL/MHL group (ITT Population)
14.1.2.5	Bar chart of the mean speech recognition (% correct words) and 95% CIs by aided, unaided and their difference, measured in quiet and in noise with the AB[s] short list test for the combined group and the CHL/MHL group (only for patients with both measurements) (ITT Population)
14.1.2.6	Boxplot and mean of the aided speech recognition (% correct words) by aided, unaided and their difference, measured in quiet and in noise with the AB[s] short list test for the combined group and the CHL/MHL group (only for patients with both measurements) (ITT Population)
14.1.3.1	Bar chart showing mean unaided and aided speech recognition score (% correct words) and 95% CIs measured in noise with the AB[s] short list test when speech is directed to the aided ear, and noise is directed to the non-implanted ear for the combined group and the SSD group (ITT Population)
14.1.3.2	Boxplot and mean of the unaided and aided speech recognition score (% correct words) measured in noise with the AB[s] short list test when speech is directed to the aided ear, and noise is directed to the non-implanted ear for the combined group and the SSD group (ITT Population)
14.1.3.3	Bar chart of the proportion with a difference >0, =0, <0 of unaided vs aided speech recognition score (% correct words) measured in noise with the AB[s] short list test when speech is directed to the aided ear, and noise is directed to

STATISTISKA KONSULTGRUPPEN		Statistical Analysis Plan	
Protocol: Investigating hearing with Ponto 3 SuperPower, a bone anchored hearing aid - Investigating hearing with Ponto 3 SuperPower, a bone anchored hearing solution.		Protocol No: BC107	Version: 1.0 Page 19 of 23

	the non-implanted ear for the combined group and the SSD group (ITT Population)
14.1.3.4	Bar chart showing mean unaided and aided speech recognition score (% correct words) and 95% CIs measured in noise with the AB[s] short list test when speech is directed to the non-implanted ear, and noise is directed to the aided ear for the combined group and the SSD group (ITT Population)
14.1.3.5	Boxplot and mean of the unaided and aided speech recognition score (% correct words) measured in noise with the AB[s] short list test when speech is directed to the non-implanted ear, and noise is directed to the aided ear for the combined group and the SSD group (ITT Population)
14.1.3.6	Bar chart of the proportion with a difference >0, =0, <0 of unaided vs aided speech recognition score (% correct words) measured in noise with the AB[s] short list test when speech is directed to the non-implanted ear, and noise is directed to the aided ear for the combined group and the SSD group (ITT Population)
14.1.4.1	Mean effective gain and 95% CIs for frequencies 500, 1000, 2000, 3000 and 4000 Hz, and PTA4 (ITT population)
14.1.4.2	SUBPLOT A: Mean aided sound field threshold and 95% CIs for frequencies 500, 1000, 2000, 3000 and 4000 Hz, and PTA4 SUBPLOT B: Mean BC in-situ threshold with Device A and 95% CIs for frequencies 250, 500, 1000, 2000, 3000, 4000, 6000 and 8000 Hz, and PTA4 (ITT population)
14.1.5	Boxplot and mean of the Glasgow Benefit Inventory (GBI) scores in each subscale (General, Social, Physical) and total score collected before and after fitting of the P3SP, for the combined group and by type of hearing loss (ITT population)
14.1.6.1	Mean and 95% CIs difference between AC and BC thresholds, denoted 'air to bone gap' (dB), calculated for frequencies 500, 1000 and 2000 Hz, and PTA3, for the combined group and the CHL/MHL group (ITT population)
14.1.6.2	SUBPLOT A: Mean AC threshold (dB HL) and 95% CIs for frequencies 250, 500, 1000, 2000, 3000, 4000, 6000 and 8000 Hz, and PTA3 SUBPLOT B: Mean BC threshold (dB HL) and 95% CIs for frequencies 500, 1000 and 2000 Hz, and PTA3, for the combined group by type of hearing loss (ITT population)
14.1.7	Bar chart showing the mean and 95% CIs Holger scores collected pro and post fitting of P3SP, for the combined group and by type of hearing loss (ITT population)
14.1.8	Bar chart showing the self-reported usage of connectivity device(s) for the combined group and by type of hearing loss (ITT population)
14.2.1.1	Mean functional gain and 95% CIs for frequencies 500, 1000, 2000 and 4000 Hz, and PTA4, for the CHL/MHL group (TP1)
14.2.1.2	Bar chart of the proportion with a difference >0, =0 and <0 of functional gain for frequencies 500, 1000, 2000, 3000 and 4000, and PTA4, for the CHL/MHL group (TP1)
14.2.1.3	SUBPLOT A: Mean unaided AC threshold and 95% CIs for frequencies 500, 1000, 2000 and Hz, and PTA4

STATISTISKA KONSULTGRUPPEN		Statistical Analysis Plan	
Protocol: Investigating hearing with Ponto 3 SuperPower, a bone anchored hearing aid - Investigating hearing with Ponto 3 SuperPower, a bone anchored hearing solution.		Protocol No: BC107	Version: 1.0 Page 20 of 23

	SUBPLOT B: Mean aided sound field threshold and 95% CIs for frequencies 500, 1000, 2000 and 4000, and PTA4 for the CHL/MHL group (TP1)
14.2.2.1	Bar chart of the mean aided speech recognition (% correct words) and 95% CIs measured in quiet and in noise with the BKB sentence test for the CHL/MHL group (TP1)
14.2.2.2	Boxplot and mean of the aided speech recognition (% correct words) measured in quiet and in noise with the BKB sentence test for the CHL/MHL group (TP1)
14.2.2.3	Bar chart of the mean aided speech recognition (% correct words) and 95% CIs measured in quiet and in noise with the AB[s] short list test for the CHL/MHL group (TP1)
14.2.2.4	Boxplot and mean of the aided speech recognition (% correct words) measured in quiet and in noise with the AB[s] short list test for the CHL/MHL group (TP1)
14.2.3.1	Mean effective gain and 95% CIs for frequencies 500, 1000, 2000, 3000 and 4000 Hz, and PTA4 (TP1)
14.2.3.2	SUBPLOT A: Mean aided sound field threshold and 95% CIs for frequencies 500, 1000, 2000, 3000 and 4000 Hz, and PTA4 SUBPLOT B: Mean BC in-situ threshold with Device A and 95% CIs for frequencies 250, 500, 1000, 2000, 3000, 4000, 6000 and 8000 Hz, and PTA4 (TP1)
14.2.4	Boxplot and mean of the Glasgow Benefit Inventory (GBI) scores in each subscale (General, Social, Physical) and total score collected before and after fitting of the P3SP for the CHL/MHL group (TP1)
14.2.5.1	Mean and 95% CIs difference between AC and BC thresholds, denoted 'air to bone gap' (dB), calculated for frequencies 500, 1000 and 2000 Hz, and PTA3, for the CHL/MHL group (TP1)
14.2.5.2	SUBPLOT A: Mean AC threshold (dB HL) and 95% CIs for frequencies 250, 500, 1000, 2000, 3000, 4000, 6000 and 8000 Hz, and PTA3 SUBPLOT B: Mean BC threshold (dB HL) and 95% CIs for frequencies 500, 1000 and 2000 Hz, and PTA3, for the CHL/MHL group (TP1)
14.3.1.1	Bar chart showing mean unaided and aided speech recognition score (% correct words) and 95% CIs measured in noise with the AB[s] short list test when speech is directed to the aided ear, and noise is directed to the non-implanted ear for the SSD group (TP2)
14.3.1.2	Boxplot and mean of the unaided and aided speech recognition score (% correct words) measured in noise with the AB[s] short list test when speech is directed to the aided ear, and noise is directed to the non-implanted ear for the SSD group (TP2)
14.3.1.3	Bar chart of the proportion with a difference >0 , $=0$, <0 of unaided vs aided speech recognition score (% correct words) measured in noise with the AB[s] short list test when speech is directed to the aided ear, and noise is directed to the non-implanted ear for the SSD group (TP2)
14.3.1.4	Bar chart showing mean unaided and aided speech recognition score (% correct words) and 95% CIs measured in noise with the AB[s] short list test when speech is directed to the non-implanted ear, and noise is directed to the aided ear for the SSD group (TP2)

STATISTISKA KONSULTGRUPPEN		Statistical Analysis Plan	
Protocol: Investigating hearing with Ponto 3 SuperPower, a bone anchored hearing aid - Investigating hearing with Ponto 3 SuperPower, a bone anchored hearing solution.		Protocol No: BC107	Version: 1.0 Page 21 of 23

14.3.1.5	Boxplot and mean of the unaided and aided speech recognition score (% correct words) measured in noise with the AB[s] short list test when speech is directed to the non-implanted ear, and noise is directed to the aided ear for the SSD group (TP2)
14.3.1.6	Bar chart of the proportion with a difference >0, =0, <0 of unaided vs aided speech recognition score (% correct words) measured in noise with the AB[s] short list test when speech is directed to the non-implanted ear, and noise is directed to the aided ear for the SSD group (TP2)
14.3.2	SUBPLOT A: Mean AC threshold (dB HL) and 95% CIs for frequencies 250, 500, 1000, 2000, 3000, 4000, 6000 and 8000 Hz, and PTA3 SUBPLOT B: Mean BC threshold (dB HL) and 95% CIs for frequencies 500, 1000 and 2000 Hz, and PTA3, for the SSD group (TP2)
14.3.3	Boxplot and mean of the Glasgow Benefit Inventory (GBI) scores in each subscale (General, Social, Physical) and total score collected before and after fitting of the P3SP for the SSD group (TP2)
14.4.1.1	Mean functional gain and 95% CIs for frequencies 500, 1000, 2000 and 4000 Hz, and PTA4, for the CHL/MHL group (TP1-Bilateral)
14.4.1.2	Bar chart of the proportion with a difference >0, =0 and <0 of functional gain for frequencies 500, 1000, 2000, 3000 and 4000, and PTA4, for the CHL/MHL group (TP1-Bilateral)
14.4.1.3	SUBPLOT A: Mean unaided AC threshold and 95% CIs for frequencies 500, 1000, 2000 and Hz, and PTA4 SUBPLOT B: Mean aided sound field threshold and 95% CIs for frequencies 500, 1000, 2000 and 4000, and PTA4 for the CHL/MHL group (TP1-Bilateral)
14.4.2.1	Bar chart of the mean aided speech recognition (% correct words) and 95% CIs measured in quiet and in noise with the BKB sentence test for the CHL/MHL group (TP1-Bilateral)
14.4.2.2	Boxplot and mean of the aided speech recognition (% correct words) measured in quiet and in noise with the BKB sentence test for the CHL/MHL group (TP1-Bilateral)
14.4.2.3	Bar chart of the mean aided speech recognition (% correct words) and 95% CIs measured in quiet and in noise with the AB[s] short list test for the CHL/MHL group (TP1-Bilateral)
14.4.2.4	Boxplot and mean of the aided speech recognition (% correct words) measured in quiet and in noise with the AB[s] short list test for the CHL/MHL group (TP1-Bilateral)
14.4.3.1	Mean effective gain and 95% CIs for frequencies 500, 1000, 2000, 3000 and 4000 Hz, and PTA4 (TP1-Bilateral)
14.4.3.2	SUBPLOT A: Mean aided sound field threshold and 95% CIs for frequencies 500, 1000, 2000, 3000 and 4000 Hz, and PTA4 SUBPLOT B: Mean BC in-situ threshold with Device A and 95% CIs for frequencies 250, 500, 1000, 2000, 3000, 4000, 6000 and 8000 Hz, and PTA4 (TP1-Bilateral)

STATISTISKA KONSULTGRUPPEN		Statistical Analysis Plan	
Protocol: Investigating hearing with Ponto 3 SuperPower, a bone anchored hearing aid - Investigating hearing with Ponto 3 SuperPower, a bone anchored hearing solution.	Protocol No: BC107	Version: 1.0	Page 22 of 23

14.4.4.1	Mean and 95% CIs difference between AC and BC thresholds, denoted 'air to bone gap' (dB), calculated for frequencies 500, 1000 and 2000 Hz, and PTA3, for the CHL/MHL group (TP1-Bilateral)
14.4.4.2	SUBPLOT A: Mean AC threshold (dB HL) and 95% CIs for frequencies 250, 500, 1000, 2000, 3000, 4000, 6000 and 8000 Hz, and PTA3 SUBPLOT B: Mean BC threshold (dB HL) and 95% CIs for frequencies 500, 1000 and 2000 Hz, and PTA3, for the CHL/MHL group (TP1-Bilateral)

STATISTISKA KONSULTGRUPPEN		Statistical Analysis Plan
Protocol: Investigating hearing with Ponto 3 SuperPower, a bone anchored hearing aid - Investigating hearing with Ponto 3 SuperPower, a bone anchored hearing solution.	Protocol No: BC107	Version: 1.0
		Page 23 of 23

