#### 9.3.3.7 Skin reaction

Classification of skin reactions around skin penetrating implants will be made using the Holgers score [8]. The Holgers classification is a scale from 0 to 4 that is used to grade skin reactions. Grade 0 indicates a reaction-free area whereas 4 indicates a severe infection often requiring removal of the implant, see table Table 6. Overview of grades of reaction on the Holger score. The Holger score is collected at the fitting and post-fitting follow up.

Holgers score	
0	No reaction
1	Erythema with slight swelling around abutment
2	Erythema, moistness and moderate swelling
3	Erythema, moistness and moderate swelling with granulation around abutment
4	Overt signs of infection resulting in removal of implant

Table 6. Overview of grades of reaction on the Holger score.

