- Holgers score (scale 0-4) assigned by investigator at fitting and post-fitting follow up (ITT / TP1 / TP2) (Objective J).

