4 STATISTICAL METHODOLOGY

4.1 General Methodology

The descriptive statistics of continuous variables will be given as Mean, standard deviation (SD), Median, Q1, Q3, Minimum, Maximum and 95% CIs. The distribution of categorical and dichotomous variables will be given as number and percentage.

Statistical tests will be performed for Functional gain (PTA-4 and frequencies), difference in speech recognition score between unaided and aided (AB[s] short list test for SSD patients), effective gain (PTA-4 and frequencies), and GBI scores (from before and after fitting).

Continuous data will be tested for normality using the Shapiro-Wilk test. Paired t-test will be performed if the data is normally distributed. Wilcoxon signed-rank test will be performed if the data is not normally distributed. For categorical change variables i.e. change <0, 0 and >0 sign test will be used to test whether the change is significant or not. Pearson's correlations (or Spearman's if the data is not normally distributed) will be used to test correlations.

All tests will be two-tailed and conducted at 0.05 significance level. All analyses will be performed by using SAS® v9.4 (Cary, NC).

All analyses will be performed on the ITT population and the Target populations (TP1 and TP2) where applicable. Subgroup analyses (combined group (CHL/MHL+SSD and SNHL if any) and the subgroups CHL/MHL & SSD) will be conducted for the ITT population. Additional analyses will be performed on one subset of the TP1:

- Bilaterally fitted Ponto 3 SuperPower users with CHL/MHL. This is to avoid any contribution from the non-Ponto 3 SuperPower fitted ear in unilaterally fitted users or bimodally users (BAHS on one ear, hearing aid on the other), since all measurements have been performed without masking or blocking of the contralateral ear.

An overview of the analysis per objective is presented in the table below.

Objectives	ITT	Target	Effect of Ponto 3 SuperPower (bilaterally fitted CHL/MHL subjects)
A	X	X (TP1)	X
B	X	X (TP1)	X
C	X	X (TP1)	X
D	X	X (TP2)	
E	X	X (TP1)	X
F	X	X (TP1)	X
G	X	X (TP1 + TP2)	
H	X	X (TP1 + TP2)	X

STATISTISKA KONSULTGRUPPEN			Statistical Analysis Plan	
Protocol: Investigating hearing with Ponto 3 SuperPower, a bone anchored hearing aid - Investigating hearing with Ponto 3 SuperPower, a bone anchored hearing solution.				Protocol No: BC107
			Version: 1.0	Page 13 of 23

I	X	X (TP1)	
J	X	X (TP1 + TP2)	

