Protocol: Investigating hearing with Ponto 3 SuperPower, a bone anchored hearing aid - Investigating hearing with Ponto 3 SuperPower, a bone anchored hearing solution.		Protocol No: BC107	Version: 1.0 Page 16 of 23

14A.4.4	Proportion with a difference >0 , $=0$ and <0 , between unaided and aided speech recognition scores (% correct words) measured in noise with the AB[s] short list test when speech is directed to the non-implanted ear, and noise is directed to the aided ear for the combined group and the SSD group (ITT Population)
14A.5	Aided sound field threshold, BC in-situ, and effective gain (aided – BC in-situ), PTA4 and all frequencies, for the combined group and the CHL/MHL group (ITT Population)
14A.6	Glasgow Benefit Inventory (GBI) scores in each subscale (General, Social, Physical) and total score collected before and after fitting of the P3SP, and their difference, for the combined group and by type of hearing loss (ITT Population)
14A.7	Sound field thresholds, PTA4 and all frequencies for AC and BC thresholds, and 'air to bone gap' (AC - BC) for the combined group and by type of hearing loss (ITT Population)
14A.8	Holger scores collected pro and post fitting of P3SP, for the combined group and by type of hearing loss (ITT Population)
14A.9	Self-reported usage of connectivity device(s) for the combined group and by type of hearing loss (ITT Population)
14B.1.1	Demographics and Baseline Characteristics by hearing loss (TP1, TP1-Bilateral)
14B.1.2	PTA4 AC and PTA4 BC audiogram for implanted and non-implanted ear by population and type of hearing loss (TP1, TP1-Bilateral)
14B.1.3	AC and BC audiograms for implanted and non-implanted ear by population and type of hearing loss (TP1, TP1-Bilateral)
14B.2.1	Unaided AC threshold, aided sound field threshold, and functional gain (unaided AC - aided), PTA4 and all frequencies, for the CHL/MHL group and the bilateral and unilateral group with only BAHS (TP1, TP1-Bilateral)
14B.2.2	Unaided AC threshold, aided sound field threshold, and functional gain (unaided AC - aided), PTA4 and all frequencies proportion with a difference >0 , $=0$ and <0 , for the CHL/MHL group and the bilateral and unilateral group with only BAHS (TP1, TP1-Bilateral)
14B.3.1	Aided speech recognition (% correct words) measured with the BKB sentence test by test condition (in quiet or in noise) for the CHL/MHL group and the bilateral and unilateral group with only BAHS (TP1, TP1-Bilateral)

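### The only Holgers figure plots an ordinal 0–4 skin grade as a mean with 95% CI, and the SAP specifies no paired change, no rule for two abutments and no Holgers listing

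*SAP*

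**What the plan says.** Objective J (protocol 8.2) is to assess the skin condition around the abutment. SAP 3.2.2 files the variable under secondary efficacy: "Holgers score (scale 0-4) assigned by investigator at fitting and post-fitting follow up (ITT / TP1 / TP2) (Objective J"). In the data collection schedule (protocol Table 5) it is the only measurement marked at both the fitting and the follow-up visit.

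Protocol 9.3.3.7 defines the grades. Grade 1 is "Erythema with slight swelling around abutment". Grade 3 adds granulation to moistness and moderate swelling. Grade 4 in Table 6 is "Overt signs of infection resulting in removal of implant".

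The planned outputs are:

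- **Figure 14.1.7** (ITT only): "Bar chart showing the mean and 95% CIs Holger scores collected pro and post fitting of P3SP". It shows all subjects together and each hearing-loss type separately.
- **Table 14A.8** (ITT): "Holger scores collected pro and post fitting of P3SP, for the combined group and by type of hearing loss (ITT Population"). Tables 14B.6.1 (TP1) and 14C.4 (TP2) have similar titles.
- **Listings 16.2.1 to 16.2.9**: none for Holgers.

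SAP 4.1 sets the reporting rule: "The distribution of categorical and dichotomous variables will be given as number and percentage". Continuous variables get mean, SD, median, quartiles, minimum, maximum and 95% CI. The SAP does not say which class Holgers belongs to. Table layouts are deferred to a separate guidelines appendix (SAP 7).

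**The concern.** The grades are ordered descriptions with no stated equal spacing. A step from 0 to 1 is slight redness and swelling; a step from 3 to 4 is infection with loss of the implant. A mean treats these steps as interchangeable, so the bar cannot say how many subjects were at each grade.

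The second gap is pairing. The GBI table is specified as "collected before and after fitting of the P3SP, and their difference, for the combined group and by type of hearing loss", and functional gain and the SSD speech scores get proportions above, at and below zero. Holgers gets neither. SAP 4.1 defines a sign test for categorical change, but Holgers is not among the variables named for testing. Missing data are expected and not imputed, and no restriction to subjects scored at both visits is stated for Holgers, although Table 14A.3.3 has one for the AB[s] test. The two bars could therefore rest on different subjects.

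Third, subjects may be fitted bilaterally on two abutments, and nothing says whether one or both scores enter, or how they combine.

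Fourth, with no listing, a high grade can be traced to a subject only through the adverse event outputs. Protocol 9.3.2 limits those to events mentioned in the audiology file within the data collection window.

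At stake is whether the report can say how many subjects had each grade of reaction, and how many got worse after fitting.

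**Working it through.** The documents give no expected Holgers rate, mean or SD, so there is no figure of the plan's own to reproduce. The counts below are assumptions chosen to show what the display can and cannot distinguish.

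**Inputs.** n = 55 (protocol 11.2, SAP 1.4), assuming one score per subject and none missing. Grades 0–4 are from protocol 9.3.3.7. All subjects not mentioned are at grade 0.

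**Formulas.** Mean = Σx/n. SD = √[(Σx² − (Σx)²/n)/(n − 1)]. 95% CI = mean ± t(0.975, n − 1) × SD/√n, with t = 2.005 for n = 55.

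**1. Same mean and same CI, different severity.**

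| | One at grade 4, eight at grade 1 | Six at grade 2 |
|---|---|---|
| Σx | 4 + 8 = 12 | 6 × 2 = 12 |
| Σx² | 16 + 8 = 24 | 6 × 4 = 24 |
| Mean | 12/55 = 0.218 | 0.218 |
| SD | √[(24 − 144/55)/54] = 0.629 | 0.629 |
| 95% CI | 0.218 ± 2.005 × 0.629/√55 = 0.048 to 0.388 | 0.048 to 0.388 |
| n (%) at grade 4 | 1 (1.8%) | 0 (0%) |
| n (%) at grade 2 | 0 (0%) | 6 (10.9%) |
| n (%) at grade 1 | 8 (14.5%) | 0 (0%) |

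Because Σx and Σx² agree, the match holds at any n. At n = 45 both give mean 12/45 = 0.267 and CI 0.060 to 0.473 (t = 2.015).

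**2. Same bar, different CI.** Three at grade 3 give Σx = 9, Σx² = 27, mean 0.164, SD 0.688, CI −0.022 to 0.350. Nine at grade 1 give Σx = 9, Σx² = 9, mean 0.164, SD 0.373, CI 0.063 to 0.265. The bars are equal, but the first interval is nearly twice as wide and runs below 0, a value the scale does not have.

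**3. Change hidden by unpaired means.** Suppose four subjects have grade 2 at fitting and four different subjects have grade 2 at follow-up. Each mean is 8/55 = 0.145 (CI 0.004 to 0.287), with four worsened and four improved. If the same four subjects stay at grade 2, the bars and CIs are identical, with none worsened and none improved. A fitting-by-follow-up table separates the two cases; Figure 14.1.7 cannot.

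**The case against.** The strongest reply is that the figure is not the whole analysis. Three tables also report Holgers, and SAP 4.1 would help whichever class applies. If Holgers is categorical, the tables give n (%) per grade and severity is visible. If it is continuous, they give the maximum, which in the first example is 4 against 2. This stands as far as it goes. Whether the tables use counts per grade can be neither confirmed nor excluded without the layout appendix. It does not supply a paired change, a unit rule or a listing.

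Second, adverse events are tabulated and listed (16.2.9) and serious ones are listed by subject, so an implant removal may surface there. That is a real but partial safeguard, since it depends on the audiology file mentioning the event within the window. The missing listing is also not peculiar to Holgers: GBI has none either.

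Several stronger readings are tempting but not supported:

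- **That a few severe grades always look the same as several mild ones.** The figure also plots CIs, and in the second calculation they differ visibly. Mean and CI coincide only for certain mixed patterns, such as the first.
- **That the figure plainly breaks the SAP's rule.** The SAP never classifies Holgers, so the inconsistency is conditional on its being categorical.
- **That the SAP scores one abutment per subject, or keeps the better one.** It is silent. The best-ear rule is written for thresholds and the gains and gaps derived from them, and nothing extends it to skin.
- **That Objective J asks for the number of new moderate or severe reactions, or that Holgers is a designated safety endpoint.** The objective says only to assess skin condition, and the SAP files the score under efficacy.

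**Conclusion.** The point holds. Figure 14.1.7 uses a summary poorly suited to an ordinal grade, and no planned Holgers output specifies a within-subject or within-abutment change, a bilateral unit or a traceable record. The size is shown by example: at an assumed n = 55, a pattern that includes one grade 4 and a pattern with nothing above grade 2 produce the same 0.218 (0.048 to 0.388), and four worsening against four improving produces no visible difference between visits. These counts are illustrative; no rate can be taken from the documents.

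The consequence is limited. This is a secondary endpoint that is not among the variables to be tested, and protocol 11.3 applies no pass/fail criterion. What is affected is the conclusion for Objective J. If the layout appendix already specifies n (%) per grade in the three tables, severity is recoverable there, and what remains is the figure, the pairing, the abutment rule and the listing.

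**What to change.** In the SAP:

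1. Replace the mean bars in Figure 14.1.7 with stacked n (%) per grade at each visit.
2. State in Tables 14A.8, 14B.6.1 and 14C.4 that the summary is n (%) per grade at each visit, with the number scored.
3. Add a fitting-by-follow-up shift table restricted to abutments with both scores, and report the number whose grade rose.
4. State the unit: each abutment is analysed, and subject-level counts for bilateral users take the worse abutment.
5. Add a Holgers listing to section 7.3, by subject, side and visit.

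The cost is SAP wording, one shift table and one listing, from scores already in the collection schedule. One dependency should be checked: the documents do not say whether the eCRF holds a separate score for each abutment. If it does not, the SAP should say so, and say which score was recorded for bilateral users.
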